11.0 Privacy/Confidentiality Issues

For the pre-post evaluation, privacy breach due to electronic exchange of information will be protected against via technical safeguards including secure transmission modes for communication, including virtual private networks (VPN) or secure sockets layer (SSL), and encryption techniques, developed and utilized in other projects by 52Inc.

The entire Memento.HTN system will use industry standard practices for access control, data security in transit, and data security at rest. The system will meet or exceed OWASP standards. All data is encrypted at rest using AES 256. All data is encrypted in transit using TLS 1.2 or 1.3 with pinned certificates where appropriate. Only users on the technical team with a direct need to view user data have access to said data and all access by the technical and/or study team will be fully logged.

Following the study, the pre-post data will be moved to a long-term storage database with Amazon Web Services and will only be accessible by EHG staff.

In the patient pre-post informed consent, we will also state that online data collected for this study will be removed from the Qualtrics platform, which is HIPAA compliant, stored in our HIPPA compliant EHG Google Drive, and backed up on encrypted folders on an EHG MacBook Pro. Passwords to access the folders will be stored in LastPass, which uses strong encryption algorithms and provides extra

security. LastPass is considered highly secure by industry standards.

12.0 Follow-up and Record Retention

Any audio recordings made will be kept in a password protected computer, separate from participant names. Access will be limited to the PI and study staff.

### **Analysis plan:**

**Measures: Primary:** HTN med adherence will be assessed by the Adherence to Refills and Medication Scale (ARMS), a well-validated self-report measure used widely in studies with minority patients and/or those with low literacy (Buis et al., 2019; Kripalani et al., 2009; McNaughton et al., 2014). We will also use Segeral et al. (2010) 3-item adherence measure, as in our prior research (Pagan-Ortiz et al., 2019). (NB: The team revised the adherence measure approach to use a single measure, namely the Wilson et al. (2016) Self-Report Medication Adherence scale.) **Secondary:** Adherence self-efficacy will be assessed with the HTN med adherence self-efficacy scale (MASES) new (Ogedegbe et al. 2003). Stress burden will be assessed using Perceived Stress Scale (Cohen et al., 1983). HTN knowledge will be assessed using the NHLBI HTN Knowledge Scale (Carter-Edwards et al., 2002). **Primary Hypothesis:** Participants will show greater HTN med adherence at 6 wks compared to baseline. **Secondary Hypothesis:** Participants will show greater HTN adherence self-efficacy, greater HTN knowledge, and lower stress burden at 6 wks compared to baseline.

**Data analyses:** We will conduct one-tailed paired t-tests at the .05 level for primary hypotheses. Data from our Phase 1 evaluation of short-term effectiveness will be used to determine the sample size necessary for an adequately-powered Phase 2 RCT.

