During the 6-week study period, patient participants will receive several types of text messages: daily interactive pill reminders, educational, motivational, spiritual/stress-supportive. Individuals that are 'new starts,' i.e. have been prescribed HTN meds within the last 8 weeks, will receive additional texts to support their implementation and persistence with their HTN med regimen. Study staff will monitor backend data to

determine if any patient participants are not opening their text messages or if a patient has missed pills 2 out of 7 days, which Dr.[name] has advised us is a clinically-significant pill lapse. In such instances, study staff will reach out to patients to see if they need support to help them with engagement.

At 6 weeks, patient participants will receive a phone call and text informing them it is time to re-take baseline assessments as well as to participate in end-of-study focus group (or individual interview). At the end of the study, participants will be invited to participate in a zoom focus group with up to 10 other participants or an individual interview (zoom or phone) to provide feedback on the Memento system.

After re-taking baselines and participating in the end-of-study focus group/interview, pre-post participants will be emailed a link for \$130 Amazon gift card.

6.0 Reporting of Adverse Events or Unanticipated Problems involving Risk to Participants or Others

We consider the risks to participants in both the patient and the healthcare provider focus groups to be minimal, i.e. there is a minor risk that other members of the patient focus group will know that a given participant is taking HTN medications. We will be clear in consenting patients that such a risk exists. There is a small risk of the time demand of the focus group will feel burdensome. We will make clear in informed consents for patients and for providers that they may end their participation at any time if the time demand becomes a problem.

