8.0 Study Withdrawal/Discontinuation

Any participant may choose to withdraw from the focus group study or the pre-post study at any time and for any reason. Participants will need simply to contact the investigator.

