9.0. Outcome Measures

HTN med adherence will be assessed by the Adherence to Refills and Medication Scale (ARMS), a well-validated self-report measure used widely in studies with minority patients and/or those with low literacy (Buis et al., 2019; Kripalani et al., 2009; McNaughton et al., 2014). We will also use Segeral et al. (2010) 3-item adherence measure, as in our prior research (Pagan-Ortiz et al., 2019). Validated self-report measures correlate with clinical outcomes and are desirable to use in research with African American patients, who may resist providing bio-specimens due to historical mistrust (Ewing et al., 2019, Stirratt et al., 2015). Lastly, electronic pill bottles are cumbersome, expensive, and often ineffective for promoting and tracking adherence (Choudhry et al., 2017; Volpp et al., 2017).

Secondary: Adherence self-efficacy will be assessed with the HTN med adherence self-efficacy scale (MASES) (Ogedegbe et al. 2003). HTN knowledge will be assessed using the NHLBI HTN Knowledge Scale (Carter-Edwards et al., 2002). Stress burden will be assessed using Perceived Stress Scale (Cohen et al., 1983). **Exploratory:** BP will be measured at baseline and 6 weeks. **Primary Hypothesis:** Participants will show greater HTN med adherence at 6 wks compared to baseline.

Secondary Hypothesis: Participants will show greater HTN adherence self-efficacy, greater HTN knowledge, and lower stress burden at 6 wks compared to baseline. **Exploratory Hypothesis:** Participants will show a decrease in systolic BP at 6 wks compared to baseline. **Data analyses:** We will conduct one-tailed paired t-tests at the .05 level for primary and exploratory hypotheses and McNemar's chi square for secondary hypotheses. Data from our Phase 1 evaluation of short-term effectiveness will be used to determine the sample size necessary for an adequately-powered Phase 2 RCT.

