10.0 Statistical Considerations

Because this is a feasibility study, the pre-post evaluation sample size is not based on power calculations. In Phase 2, a sample size will be created with a power of at least 90% with a two-sided alpha level of .05.

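### The planned paired t-test describes only participants who complete the week-6 assessment, yet its estimate is to inform Phase 2 sizing; an all-enrolled analysis with one sensitivity analysis is a cheap improvement

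*SAP*

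**What the plan says.** The SAP (Analysis plan, Data analyses) gives one analysis for the primary hypothesis: "We will conduct one-tailed paired t-tests at the .05 level for primary hypotheses". Protocol section 9.0 agrees: "We will conduct one-tailed paired t-tests at the .05 level for primary and exploratory hypotheses". The hypothesis is a within-person comparison in a single arm: "Participants will show greater HTN med adherence at 6 wks compared to baseline". The SAP notes a change to a single self-report adherence scale, which does not affect this point.

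Neither document states an analysis population, a missing-data method, a sensitivity analysis, an expected dropout rate or a comparison of completers with non-completers. Section 10.0 says that "the pre-post evaluation sample size is not based on power calculations".

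Three other places bear on who has a week-6 score:

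- Section 8.0: "Any participant may choose to withdraw from the focus group study or the pre-post study at any time and for any reason".
- Section 5.0: staff monitor the system to "determine if any patient participants are not opening their text messages" or have missed pills on 2 of 7 days, and then contact them. At 6 weeks participants are telephoned and texted to repeat the assessments.
- Sections 5.0 and 7.0: $130 of the $150 compensation comes at the end of the study, after the repeat assessments and the closing focus group or interview.

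On use of the result, section 9.0 says: "Data from our Phase 1 evaluation of short-term effectiveness will be used to determine the sample size necessary for an adequately-powered Phase 2 RCT". The SAP repeats this. Section 10.0 sets Phase 2 at a minimum of 90% power with a two-sided alpha of .05.

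**The concern.** A person with a baseline score but no week-6 score contributes nothing to a paired t-test. If anyone is lost, the test answers a question about completers, while Aim 2 concerns short-term effectiveness in the people given the system. In a study of a texting tool it is plausible, though not established, that those lost differ from those who return, either in baseline adherence or in how much they changed. There is no control arm in which similar losses might partly offset this.

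The consequence reaches beyond the pilot because Phase 1 data are to inform the Phase 2 sample size. If the completers' change overstates the change in all enrolled and is carried forward as the effect size, Phase 2 would fall short of its 90% power target.

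**Working it through.** The documents give no pilot N, dropout rate, effect size or SD, so there is no stated figure to reproduce. Everything below is illustrative and uses assumed inputs, except the Phase 2 power (90%) and two-sided alpha (.05) from section 10.0.

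**1. Completers against all enrolled.** Let q be the fraction without a week-6 score, Dc the mean change in completers and Dn the mean change in non-completers, scored so that higher is better. The all-enrolled change is Da = (1 − q)·Dc + q·Dn. The overstatement is Dc/Da, which is 1/(1 − q) if Dn = 0 and 1/(1 − q/2) if Dn is half of Dc.

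| Assumed loss q | Dn = 0 | Dn = half of Dc | Dn = Dc |
|---|---|---|---|
| 10% | 1/0.90 = 1.11 | 1/0.95 = 1.05 | 1 |
| 20% | 1/0.80 = 1.25 | 1/0.90 = 1.11 | 1 |
| 30% | 1/0.70 = 1.43 | 1/0.85 = 1.18 | 1 |

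If non-completers improved more than completers, the ratio falls below 1.

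**2. What this could mean for Phase 2.** Suppose, as an assumption, that the pilot change is used directly as the between-arm difference d in SD units. Then n per arm = 2(1.960 + 1.282)²/d² = 21.02/d².

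- Completer effect d = 0.5: 21.02/0.25 = 84.1, so 85 per arm.
- Dn = 0: d = 0.45, 0.40 or 0.35 at 10%, 20% or 30% loss, needing 104, 132 or 172 per arm.
- Dn = half of Dc: 94, 104 or 117 per arm.
- Dn = Dc: 85 per arm.

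With Dn = 0, the power of a trial sized on the completer effect is Φ(3.242(1 − q) − 1.960) = 83%, 74% or 62%. Ordinary dropout inflation does not repair this: 85/0.80 = 106.25, so 107 per arm, against 132 needed at 20% loss.

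**3. What a likelihood model corrects.** With two time points and complete baselines, the model's estimate of mean change is Dc + (1 − b)(Xc − Xall). Here b is the completers' slope of week-6 score on baseline, and Xc and Xall are the baseline means of completers and of all enrolled.

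- No loss: Xc = Xall, and the estimate is the paired mean difference.
- Loss related to baseline: take no true change, b = 0.6 and completers starting 0.2 SD below all enrolled. The completers' change is then biased by 0.4 × 0.2 = 0.08 SD, and the correction term removes it. Simulations with baseline-dependent loss and a correlation of 0.6 gave a completer bias of 0.08 to 0.09 SD, and under 0.01 SD with the model.
- Loss unrelated to baseline but related to the unseen change: Xc ≈ Xall, so the correction is about zero. In a simulation with 20% zero-change dropouts (true change 0.40 SD), completers and model both gave 0.498 SD.

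**4. What the zero-change analysis adds.** Its estimate is (1 − q)·Dc, which equals Da when non-completers truly do not change. It is not a lower bound. Take 30 enrolled, 24 completers at +0.15 SD and 6 dropouts at −0.6 SD, so that the true mean is (24 × 0.15 − 6 × 0.6)/30 = 0. The zero-change estimate is 0.8 × 0.15 = 0.12 SD. In that scenario the one-tailed 5% test rejects at about 1 − Φ(1.645 − 0.15√24) = 1 − Φ(0.910) = 18%. Simulation gave 17% to 18% for the paired test and about 16% for the likelihood model. The zero-change analysis does not restore the error rate either.

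**The case against.** The strongest reply has four parts.

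- **The plan is silent rather than wrong.** Naming a test does not settle how absent scores are handled, and a paired t-test can follow imputation. That is true in general. But neither document mentions imputation, and the named test applied as written uses complete pairs.
- **The protocol works to retain people.** It provides outreach to those who lapse, a telephone call as well as a text at week 6, and most of the payment after re-assessment. This stands: loss may be small. It does not say what is done with the scores that remain missing.
- **The Phase 2 harm is conjecture.** This largely stands. No sizing formula is given, and a single-arm change is not a between-arm difference. The Phase 2 figures show sensitivity and are not a forecast.
- **Complete-pairs analysis is ordinary in a small feasibility pilot.** This also stands, and it limits the weight of the point. It does not remove it, because the estimate has a declared later use.

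A reader might infer that the result rests only on people who stayed engaged, or that the gain must be biased upward. The documents do not support either. Someone can ignore the texts and still answer the call and complete the assessment, and monitoring for unopened texts is not a forecast that they will occur. There is no bias if non-completers change as completers do, and loss related to baseline can act in either direction. A reader might also suppose that the model alone would remove the overstatement in the table; step 3 shows that it would not.

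**Conclusion.** The point holds in a limited form. As written, the primary analysis estimates change among participants who complete the week-6 assessment, and that estimate is to inform Phase 2. Neither the size nor the direction of any bias can be derived from the documents. The 1.11-, 1.25- and 1.43-fold figures depend on an assumed loss of 10%, 20% or 30% and on no change in non-completers. With half the completers' gain they fall to 1.05, 1.11 and 1.18, and with equal gain there is no overstatement. The Phase 2 figures further assume that the pilot change is used directly as the RCT effect. This is a worthwhile and inexpensive improvement to the plan, not a defect that invalidates the pilot.

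**What to change.** In the SAP and Protocol section 9.0:

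- Define the primary analysis set as all enrolled participants with a baseline adherence score.
- Analyse it with a likelihood-based repeated-measures model with time as a fixed effect and correlated within-person scores. This matches the paired t-test when data are complete. State that it corrects loss related to baseline score but not loss related to the unseen week-6 score.
- Add a sensitivity analysis that assigns zero change to participants without week-6 data. Present it as a planning value, not as a worst case or a corrected test.
- Report the numbers enrolled and analysed, with baseline scores by completion status.
- Plan Phase 2 over the range from the model estimate to the zero-change estimate.

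The cost is about one paragraph in each document and a little more analysis. No new data are needed. The reported change may be less favourable than the completers' figure.
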